COPE	Coping Orientation to Problems Experienced
COPE-NVI	COPE, nuova versione italiana
CRA	Clinical Research Associate
CRO	Contract Research Organization
eCRF	Case Report Form elettronica
GAD-7	General Anxiety Disorder
GCP	Good Clinical Practice
GDPR	General Data Protection Regulation
HbA1c	Glycated Hemoglobin
IC	Informed Consent
ICH	International Conference on Harmonisation
IRB/IEC	Institutional Review Board/Independent Ethics Committee
ISF	Investigator's Site File
NPL	Neuro-Linguistic Programming
PHQ	Patient Health Questionnaire
PSESDM	Parental Self-Efficacy for the Management of Diabetes Mellitus
PSI-SF	Parental Stress Index Short-Form
T1DM	Type 1 Diabetes Mellitus
TAR	Time above range
TBR	Time below range
TIR	Time in range
TMF	Trial Master File

STUDY SYNOPSIS

Titolo	BODY EMOTIONAL MAP METHOD FOR THE REDUCTION OF PARENTAL STRESS RELATED TO DIABETES: A RANDOMIZED STUDY
Version #	2.1
Date	July 26 th 2023
Project start date	2023
Project end date	2024
Project type	National multicenter randomized controlled trial.
Staff involved	Psychologists: [name] (AN), [name] (PD), [name] (AN) Counselor: [name] (AN) Principal Investigator: [name] (AN) Doctors, dieticians and nurses of the participating teams Statisticians: [name], [name] (PE)
Background	Type 1 diabetes (T1D) in childhood and adolescence is a chronic condition characterized by significant management complexity, requiring essential therapeutic and behavioral synergy between parents and the affected child. In chronic illnesses where cure is not achievable, the therapeutic goal shifts to adaptation that allows for a good quality of life. The onset of diabetes in a child or adolescent is a critical, potentially traumatic event, also for parents, since it immediately becomes evident that they are embarking on a long journey of living with a chronic condition. A good adaptation, which in this context can be considered as the "cure" of the chronic disease, is the primary goal of therapeutic intervention. The process toward adaptation varies in duration; achieving it is not guaranteed and should be viewed as an ongoing process. During this journey, obstacles are encountered that require activating resources, which can be considered "internal" to the individual or "external," related to technology, family environment, social context, and healthcare. In the phase of good adaptation, parents experience an improved state of psycho-physical well-being, fewer worries related to diabetes, positive mental representations, increased confidence in their child's future, and a stronger sense of self-efficacy. Optimal use of technology is a key factor in this process. In a preliminary pre-post, single-arm study, the BEM (Body Emotional Maps) method demonstrated the ability to reduce parental stress measured after three months using the Parental Stress Index Short-Form (PSI-SF).
Objectives	The purpose of this study is to evaluate the impact of the BEM method on stress and well-being in parents of children/adolescents with type 1 diabetes, compared to a standard group approach focused on therapeutic education (control group).
Inclusion criteria	
 ▪ Parents of children and adolescents under 18 years old with type 1 diabetes, with a duration of diabetes > 12 months.

	
 ▪ Parents of children who have never been diagnosed with psychiatric or behavioral disorders. Adequate understanding of the Italian language according to the clinician's judgment. ▪ Parents willing to: 
 - Be actively involved in group experiential activities; - Complete the required questionnaires. ▪ Signed informed consent from the participating individual. ▪ Signed informed consent for the processing of the minor's data by both parents (if applicable).
Exclusion criteria	
 ▪ Parents: 
 - With psychiatric conditions; - Of patients with psychiatric problems or behavioral disorders; - With any issue that, according to the clinician's judgment, precludes active participation in group experiential activities.
Experimental group: BEM	
The BEM Program involves an experiential, group-based approach facilitated by 2–3 trained facilitators and a maximum of 25 parent participants.
 
Structure of a BEM Session: each session takes place over three consecutive days and includes both plenary sessions with the entire group and smaller subgroup activities.
 
Context: it is essential to conduct the program in a setting that is removed from participants' everyday life, ideally immersed in nature. This promotes emotional distancing from daily stressors, providing a sense of isolation and tranquility conducive to deep personal work.
 
Setting: a reserved, welcoming, and intimate room is required to support a safe and comfortable environment.
 
Methodology: relaxation techniques, breathing exercises, and guided visualizations NLP (Neuro-Linguistic Programming) techniques: spatial anchoring, Time Line therapy, and future pacing. Approaches based on Transactional Analysis (T.A.) and Systemic-Relational frameworks, brief interventions focused on problem-solving. Techniques for enhancing bodily and emotional awareness. Interactive group discussions.

Control group: TRADITIONAL	
The control intervention will take place during a camp specifically dedicated to parents, with the same duration as the BEM program. The intervention includes educational and informational sessions on key aspects of type 1 diabetes management (management of acute complications, importance of glycemic indices, carbohydrate counting, current and emerging perspectives in type 1 diabetes care) In addition, the program includes opportunities for parents to share personal experiences and participate in recreational activities.

Study endpoint	
 ▪ The primary endpoint is the change in the Parental Stress Index Short Form (PSI-SF) score at 3 months following participation in the group activities, compared to baseline. ▪ Secondary endpoints include: 
 - Change in PSI-SF score at 6 months after participation, compared to baseline; - Change in the scores of the individual PSI-SF subscales (Parental Distress, Parent-Child Dysfunctional Interaction, and Difficult Child) at 3 and 6 months post-intervention, compared to baseline;

	
 - Change in the Patient Health Questionnaire-9 (PHQ-9) score for the assessment of depressive symptoms at 3 and 6 months post-intervention, compared to baseline; - Change in the Generalized Anxiety Disorder-7 (GAD-7) score for the assessment of anxiety symptoms at 3 and 6 months post-intervention, compared to baseline; - Change in the Brief Pittsburgh Sleep Quality Index (B-PSQI) score for the evaluation of sleep disturbances at 3 and 6 months post-intervention, compared to baseline; - Change in the Parental Self-Efficacy for the Management of Diabetes Mellitus (PSESDM) score assessing parents' perceived self-efficacy in managing diabetes at 3 and 6 months post-intervention, compared to baseline; - Change in the Coping Orientation to the Problems Experienced – New Italian Version (COPE-NVI) score for the evaluation of parental adaptation and coping strategies at 3 and 6 months post-intervention, compared to baseline; - Change in children's/adolescents' glycemic metrics (including glycemic variability, Time in Range [TIR], Time Above Range [TAR], Time Below Range [TBR], and HbA1c) at 3 and 6 months after the intervention, compared to baseline. 
▪ Additionally, a qualitative analysis will be conducted to explore unmet parental needs.

Study procedure	
After verification of eligibility criteria, parents will be randomly web-based randomization to either the BEM group intervention or the control group intervention. If both parents are eligible, they will be allocated to the same study arm.
 
Randomization will be stratified by study center.
 
Upon obtaining informed consent, parents will receive login credentials for the study's web platform, through which they will complete the required questionnaires. At enrollment, socio-demographic data of the parents and clinical data related to the child/adolescent will also be collected.
 
Parents will then be invited to participate in either the BEM group intervention or the standard group intervention. Both group activities will be conducted under the supervision of trained healthcare personnel and will have the same duration, although their content will differ.
 
(Non-specialized healthcare personnel will receive specific training in a two-day weekend course (8 hours per day) led by professionals experienced in the BEM methodology).
 
Specifically, the BEM group will receive basic information on diabetes management using external resources (medical support, technology, telemedicine, carbohydrate counting techniques) and internal resources (learning effective techniques and behaviors to improve metabolic control). This will be followed by the experiential BEM-specific program.
 
The control group will receive the same diabetes management information, combined with opportunities for parent discussion and recreational activities.
 
Each group activity will include 25 parent participants.

	At 3 and 6 months following the group intervention, parents will be asked to complete the same questionnaires again via the web platform. Glycemic data for the children/adolescents will be retrieved from electronic medical records.
Statistical aspects	
Sample Size Estimation
 
 - The difference between the two groups in changes in PSI-SF scores (primary endpoint) will be expressed in terms of effect size (i.e., the difference in mean scores between groups divided by the common standard deviation at baseline). An effect size of at least 0.5 is widely accepted in the literature as clinically relevant. In a previous study [13], baseline PSI-SF scores were 75.4 ± 2.5, indicating that an effect size of 0.5 corresponds to a between-group difference of 1.25. To detect an effect size of at least 0.5 with 80% statistical power ($\alpha = 0.05$), a minimum of 64 parents per group is required. Assuming a dropout rate of 15%, a total of 150 parents (75 per group) will be enrolled. 
Data Analysis
 
 - Descriptive statistics will be reported as mean and standard deviation or, in the case of non-normally distributed continuous variables, as median and interquartile range. Categorical variables will be reported as percentages. - Between-group comparisons for descriptive variables will be conducted using the Student's t-test or the Mann-Whitney U test for continuous variables, and the chi-square test for categorical variables. - Comparisons between study arms will be performed using Mixed Models for Repeated Measures (MMRM), including the baseline value of the outcome as a linear covariate and study arm as a fixed effect. MMRMs account for both within-subject and between-subject correlations using a first-order autoregressive (AR(1)) variance-covariance structure. Similarly, comparisons between study arms for secondary endpoints, including questionnaire scores and glycemic metrics (change from baseline at 3 and 6 months), will also be conducted using MMRMs. These models will include baseline values of the respective outcomes as linear covariates and the study arm as a fixed effect. Results will be reported as estimated means with corresponding 95% confidence intervals. - Subgroup analyses will also be conducted based on parental sex and child/adolescent age (<10 years vs. ≥ 10 years).
Participating Sites	Participation is planned for six pediatric diabetes centers. Enrollment will be competitive.
Ethics aspects	The study protocol will be submitted for approval to the Ethics Committees of the participating centers.

KEY ROLES AND CONTACTS

1. INTRODUCTION: SCIENTIFIC RATIONALE

Type 1 diabetes (T1D) in pediatric and adolescent populations represents a chronic condition characterized by significant management complexity, requiring essential therapeutic and behavioral synergy between parents and the affected child (1).

The parent's need to possess awareness and management skills regarding their child's illness is fundamental to ensuring that the child achieves optimal glycemic and metabolic control and to preventing or appropriately managing potential disease-related complications (2,3). In particular, the daily requirement of insulin therapy entails passive acceptance of the inherent risks associated with the treatment, notably the potential occurrence of hypoglycemic episodes (4–6).

From the moment of diagnosis, parents must be adequately trained on the necessity of promptly initiating interventions to resolve hypoglycemic crises, should they occur in their severe form, to prevent serious complications that could lead to adverse outcomes (7).

Another serious complication of T1D is diabetic ketoacidosis (DKA) (4,8). In this context, parents must be knowledgeable about this complication and its possible manifestations to recognize it promptly and to implement the necessary therapeutic procedures (9).

All these factors contribute to a high level of distress among parents, which can further impair the management of their child's disease (10,11).

Despite the objective consensus that the most traumatic moment for parents is the diagnosis of their child's T1D, it is certainly plausible that the adaptation process to the child's condition is highly subjective and can vary in duration over time (12). In chronic illness, where cure is not achievable, the primary goal of therapeutic intervention becomes adaptation, enabling the attainment and maintenance of a good quality of life. However, achieving adaptation is not guaranteed. Throughout the process aimed at reaching it, obstacles and resources are encountered that significantly influence the possibility of adaptation. Obstacles and resources can, in turn, be considered either "internal" to the individual or "external," related to the family, social, and healthcare environment. During the phase of successful adaptation, parents experience a greater sense of psychological and physical well-being, fewer concerns related to diabetes, positive mental representations, increased confidence in their child's future, and a stronger sense of self-efficacy. In the field of diabetology, but not only, educational approaches aimed at learning and reinforcing knowledge related to the management of this chronic disease have been implemented and improved over time. Among these, the so-called "summer camps" are certainly noteworthy; these are designed for children and adolescents with T1D who participate either alone or accompanied by their parents. Obstacles and resources can, in turn, be considered either "internal" to the individual or "external," related to the family, social, and healthcare environment. During the phase of successful adaptation, parents experience a greater sense of psychological and physical well-being, fewer concerns related to diabetes, positive mental representations, increased confidence in their child's future, and a stronger sense of self-efficacy. In the field of diabetology, but not only, educational approaches aimed at learning and reinforcing knowledge related to the management of this chronic disease have been implemented and improved over time. Among these, the so-called "summer camps" are certainly noteworthy; these are designed for children and adolescents with T1D who participate either alone or accompanied by their parents.

The areas addressed during these interventions primarily concern clinical aspects related to the management of situations in which the child or adolescent is the main actor. The parents' perspective regarding their feelings about their child's illness and the potential impact on their quality of life is sometimes considered marginal. The experiential group process for parents can more specifically target these areas, helping to

improve adaptation to the child's particular condition. The BEM (Body Emotional Maps) program involves an experiential, group-based approach with the participation of 2-3 facilitators and the parents of children affected by chronic illness. It includes techniques such as relaxation, breathing exercises, guided visualizations; NLP (Neuro-Linguistic Programming) techniques like spatial anchoring, timeline work, future pacing; brief problem-solving interventions; body and emotional awareness techniques; and interactive discussions (13).

By applying the BEM methodology, it is expected that parents will improve their adaptation to their child's illness, process the trauma associated with the diagnosis, and enhance their quality of life by reducing distress and fear related to hypoglycemia.

In a preliminary pre-post, single-arm study, the BEM method demonstrated the ability to reduce parental stress, as measured by the Parental Stress Index Short-Form (PSI-SF), after three months (13).

2. STUDY OBJECTIVES

2.1 Objectives of the study

The aim of this study is to evaluate the impact of the BEM method on stress and well-being in parents of children/adolescents with type 1 diabetes, in comparison to a standard group approach focused on therapeutic education (control group).

2.2 Study Endpoint

2.2.1 Primary

The primary endpoint is represented by the difference in PSI-SF (Parental Stress Index Short-Form) scores after 3 months of participation in the group activities compared to baseline.

2.2.2 Secondary

- Difference in PSI-SF (Parental Stress Index Short-Form) scores after 6 months of participation in the group activities compared to baseline;
- Difference in the scores of the individual components of the PSI-SF questionnaire (Parental Distress, Parent-Child Dysfunctional Interaction, Difficult Child) after 3 and 6 months of participation in the group activities compared to baseline;
- Difference in the scores of the Patient Health Questionnaire (PHQ-9) for the assessment of depression and depressive symptoms after 3 and 6 months of participation in the group activities compared to baseline;
- Difference in the scores of the General Anxiety Disorder (GAD-7) questionnaire for the assessment of anxiety and anxious symptoms after 3 and 6 months of participation in the group activities

compared to baseline;

- Difference in the scores of the Brief Pittsburgh Sleep Quality Index (B-PSQI) for the assessment of sleep disturbances after 3 and 6 months of participation in the group activities compared to baseline;
- Difference in the scores of the Parental Self-Efficacy for the Management of Diabetes Mellitus (PSESDM) questionnaire for the evaluation of self-efficacy perception in managing their child's diabetes after 3 and 6 months of participation in the group activities compared to baseline;
- Difference in the scores of the Coping Orientation to the Problems Experienced - Italian Version (COPE-NVI) questionnaire for assessing parental adaptation and coping strategies after 3 and 6 months of participation in the group activities compared to baseline;
- Difference in glucometric data of children/adolescents (variability, Time In Range [TIR], Time Above Range [TAR], Time Below Range [TBR], HbA1c) after 3 and 6 months of participation in the group activities compared to baseline;
- Additionally, a qualitative analysis will be conducted to further explore parents' experiences regarding their perception of their child (e.g., "How do I see my child's life now?").

3 STUDY DESIGN

A randomized, controlled, two-arm, open-label trial. Following verification of eligibility criteria, parents will be assigned via centralized web-based randomization to participate in either the BEM group activity or the control group. In cases where both parents are eligible, they will be allocated to the same study arm.

3.1 Study duration and participating clinical sites

The study includes a 6-month follow-up after participation in the group activity.
Six pediatric diabetology sites will participate in the study.

4 STUDY POPULATION

4.1 Inclusion criteria

- Parents of children and adolescents under 18 years of age with type 1 diabetes duration exceeding 12 months
- Parents of children who have never been diagnosed with psychiatric or behavioral disorders
- Adequate understanding of the Italian language, as assessed by the clinician
- Parents willing to:
 - Actively participate in group experiential activities
 - Complete the required questionnaires
 - Signed informed consent from the participating individual
 - Signed informed consent for data processing of the minor by both parents (if applicable)

4.2 Exclusion criteria

- Parents:
 - with psychiatric conditions
 - of patients with psychiatric issues or behavioral disorders
 - with any problem that, according to the clinician's judgment, would prevent active participation in group experiential activities

4.3 Procedures for assigning interventions in the study

4.3.1 Randomization procedure

After verification of the eligibility criteria, the parents will be assigned via centralized web-based randomization to participate in either the BEM group activity or the control group (1:1 randomization). In cases where both parents are eligible, they will be allocated to the same study arm. The randomization will be stratified by center.

4.3.2 Masking procedure

The study will be conducted in an open-label design.

5 STUDY INTERVENTION

Both study groups (BEM method and control) will participate in activities conducted over three consecutive days at an off-hospital location, in contact with nature. Both group activities will be carried out under the supervision of specially trained healthcare personnel and will have equal duration, although the content will differ.

The non-specialist staff supervising the school camps will undergo appropriate training during a weekend course lasting two days (8 hours per day). The course will be conducted by experienced professionals in the BEM method.

5.1 Description of the BEM method

In the BEM group, participants will receive basic information on diabetes management through external resources (medical support, technology, telemedicine, carbohydrate counting techniques) and internal resources (learning effective techniques and behaviors to improve metabolic control). Subsequently, the specific experiential BEM program will be initiated. The BEM method involves an intervention with the parents of children with diabetes, conducted in group settings, aimed at facilitating parents' adaptation to their child's "diabetes condition" (13). The intervention is organized into three sessions.

The first session consists of an introduction and group formation.

The second session involves sharing the onset of diabetes, identifying the most critical daily challenges, and the primary change the participants wish to implement.

The third session features the BEM pathway, which includes guided visualization and the creation of a map with spatial anchors. This final session is conducted partly in a plenary setting and partly in small groups, allowing each participant the necessary time to connect with their deeper parts and express themselves. A description of the operational phases of the BEM method is included in Appendix 1 of this study protocol.

5.2 Description of the control method

In the control group, basic information on diabetes management will be provided through external resources (medical support, technology, telemedicine, carbohydrate counting techniques) and internal resources (learning effective techniques and behaviors to improve metabolic control). The control group will receive the same diabetes management information, accompanied by parent discussion sessions and recreational activities guided by the diabetes team staff. As with the BEM group, activities will take place over three days in an off-hospital location, in contact with nature. Each group activity will involve 25 parents.

STUDY PROCEDURES

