7 STATISTICAL CONSIDERATIONS

7.1 Sample Size Calculation

The primary endpoint is the PSI-SF questionnaire score at 3 months after the completion of group activities. The primary efficacy assessment will therefore involve comparing the differences in PSI-SF scores at 3 months relative to baseline between the study arms.

The difference between the two groups in changes of PSI-SF scores will be expressed in terms of effect size (the difference in scores between the two groups divided by the common standard deviation at baseline). It is widely accepted in the literature that an effect size of at least 0.5 can be considered clinically relevant [27]. From the previous study [13], baseline PSI-SF values were 75.4 ± 2.5 ; therefore, an effect size of 0.5 would correspond to a difference of 1.25 between groups.

To detect an effect size of at least 0.5 with a statistical power of 80% ($\alpha=0.05$), at least 64 parents per group need to be evaluated. Assuming a dropout rate of 15%, a total of 150 parents will be enrolled (75 per group)

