7.2 Statistical Analysis

All subjects enrolled in the study will be included in the analysis.

Descriptive data will be expressed as means and standard deviations or as medians and interquartile ranges for continuous variables, and as percentages for categorical variables.

Group comparisons for descriptive variables will be performed using Student's t-test or the Mann-Whitney U test for continuous variables, and the chi-square test for categorical variables.

Regarding the primary endpoint (difference in PSI-SF scores at 3 months compared to baseline), the comparison between study arms will be conducted using mixed-effects models for repeated measures (MMRM), which will include the baseline outcome value as a linear covariate and the study arm as a fixed effect. MMRM accounts for within- and between-subject correlations through a variance-covariance matrix with an autoregressive order 1 structure.

Similarly, comparisons between study arms for secondary endpoints related to questionnaire scores and glucometric measures (differences at 3 and 6 months compared to baseline) will be performed using MMRM.

These models will include the baseline value of the respective outcomes as a linear covariate and the study arm as a fixed effect. Results will be expressed as estimated means with 95% confidence intervals.

In addition to the analysis of the entire sample, subgroup analyses will be conducted separately based on parent sex and children/adolescents' age (<10 years and ≥ 10 years).

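### Parents attend shared camps of 25, but the sample size and the primary model treat them as independent; any within-camp correlation raises the type I error above 5% and lowers the stated 80% power

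*Protocol*

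**What the plan says.** Parents are randomised 1:1, stratified by centre, to one of two three-day group activities held away from the hospital (Protocol sections 4.3.1 and 5).

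- **Group size.** The synopsis, under Study procedure, describes both arms and then states: "Each group activity will include 25 parent participants". Section 5.2 repeats it: "Each group activity will involve 25 parents". The synopsis entry for the BEM programme instead gives "a maximum of 25 parent participants".
- **Delivery.** BEM groups have 2–3 facilitators and work partly in plenary and partly in small groups. Control groups have discussion and recreation led by diabetes-team staff, whose number is not given.
- **Sample size.** For an effect size of 0.5, 80% power and α = 0.05, section 7.1 says "at least 64 parents per group need to be evaluated". With 15% dropout this becomes 75 enrolled per arm, 150 in all. No ICC or design effect appears.
- **Model.** Section 7.2 names the baseline value and study arm, and adds: "MMRM accounts for within- and between-subject correlations through a variance-covariance matrix with an autoregressive order 1 structure". Camp and facilitator are not mentioned.

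**The concern.** Parents in one camp share facilitators, place, dates and discussion, and in the BEM arm the group work is part of the intended mechanism. Their later PSI-SF scores may therefore be correlated. Each camp belongs wholly to one arm, so camp-to-camp variation goes into the arm contrast.

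An AR(1) matrix describes how one parent's ordered visits correlate. It leaves the covariance between two different parents at zero. The statement in section 7.2 that between-subject correlation is handled is therefore wrong for parents in the same camp.

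At stake are the error rate and the confidence interval of the primary comparison, and the power claim that justifies enrolling 150 parents. This is separate from the placement of couples in the same arm, which is a further source of correlation not counted in the figures below.

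**Working it through.** **1. The plan's own figure.** Inputs from section 7.1: effect size 0.5, power 80%, α = 0.05 (two-sided reproduces the result). A two-sample t-test with 64 independent parents per arm has 80.1% power, so the stated 64 is reproduced. After dropout, 75 × 0.85 = 63.75 per arm remain, so there is no slack.

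**2. Number of camps.** 75 / 25 = 3 per arm. Evaluable parents per camp: m = 64 / 3 = 21.3.

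**3. Assumption.** The documents give no camp ICC. The range 0.01 to 0.10 is assumed.

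**4. Formulas** (outcome in SD units, equal camps):
- Design effect: DE = 1 + (m − 1) × ICC
- Correct standard error of the arm difference: SE = √(2 × DE / 64)
- Type I error of the analysis that ignores camp: 2 × [1 − Φ(1.96 / √DE)]
- Power: two-sided noncentral t with noncentrality 0.5 / SE, on 126 df (large-sample reference) or 4 df (six camps minus two arms)

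Example at ICC 0.05: DE = 1 + 20.33 × 0.05 = 2.02. SE = √(2 × 2.017 / 64) = 0.251. Noncentrality = 0.5 / 0.251 = 1.99, giving power of 51%. Type I error: 1.96 / √2.017 = 1.38, giving 17%.

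**5. Three camps per arm:**

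| ICC | DE | Effective n per arm | Type I error, camp ignored | Power, 126 df | Power, 126 df, baseline correlation 0.5 | Power, 4 df |
|---|---|---|---|---|---|---|
| 0 | 1.00 | 64 | 5% | 80% | 90% | 57% |
| 0.01 | 1.20 | 53 | 7% | 73% | 84% | 50% |
| 0.02 | 1.41 | 46 | 10% | 66% | 78% | 44% |
| 0.05 | 2.02 | 32 | 17% | 51% | 63% | 33% |
| 0.10 | 3.03 | 21 | 26% | 36% | 46% | 24% |

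A simulation of 20,000 trials with camps of 21, 21 and 22, analysed by a t-test that ignores camp, gave type I errors of 7.4 / 10.0 / 16.8 / 26.3% at the four non-zero ICCs.

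The baseline column assumes a correlation of 0.5 between baseline and 3 months and multiplies the whole variance by 1 − 0.5² = 0.75. It is an upper figure, because it shrinks the camp component too, although camp effects arise after baseline.

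**6. Smaller camps.** With 6 camps per arm, m = 64 / 6 = 10.7. At ICC 0.05, DE = 1 + 9.67 × 0.05 = 1.48, type I error is about 11%, and unadjusted power is about 63% (64% by the normal approximation), or about 55% on 10 df. At ICC 0 the power on 10 df is 72%.

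**The case against.** Several points on the other side stand.

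- **The size is conditional.** No ICC is given. At ICC 0 the stated power is correct.
- **Baseline adjustment is planned.** Section 7.1 takes no credit for it. At an assumed correlation of 0.5 it recovers power to about 84% at ICC 0.01 and 78% at 0.02, but not at 0.05 or above. Because the model still ignores camp, it does not cure the type I error.
- **The 4-df figures are largely the price of the remedy.** Power on 4 df is 57% even with no clustering, so those figures should not be quoted as the loss due to camps.
- **An analysis plan could add a camp term.** The term list in section 7.2 is not exhaustive; it names no visit effect, for example. But the protocol itself fixes the sample size without a design effect and asserts that AR(1) deals with between-subject correlation. A later document would have to contradict that assertion, and it could not restore the power claim.

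Three stronger readings are tempting but unsupported.

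- A reader might infer that camp effects bias the result towards BEM. The mechanism is an understated standard error; systematic bias would require facilitator quality to differ by arm, and the protocol does not say so.
- A reader might infer that every camp of 25 has to combine several centres, so that centre cannot stand in for camp. The synopsis makes enrolment competitive and also words the BEM size as a maximum, so a large centre might fill a camp alone.
- A reader might infer that a single staff member or team runs the control camps. Section 5.2 gives no number.

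**Conclusion.** The structural point holds. Both arms are delivered in shared groups, the sample size assumes independent parents with nothing in reserve, and the stated model cannot carry within-camp correlation although section 7.2 says it does. On the protocol's own unadjusted calculation, 80% power holds only at ICC 0.

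For an assumed ICC of 0.01 to 0.10 and three camps per arm, the type I error ignoring camp runs from about 7% to 26%. Power with the correct variance runs from about 73% to 36% unadjusted, and from at most about 84% to 46% with a baseline correlation of 0.5. More and smaller camps lessen the problem but do not remove it. Confidence is high in the structure; the magnitude rests on the assumed ICC, the assumed baseline correlation and the derived number of camps.

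**What to change.** 1. **Section 7.1 and synopsis.** Replace the unqualified 80% with the power of the planned 150 parents over a stated ICC range and number of camps per arm, taking account of the baseline covariate.
2. **Section 7.2 and synopsis.** Correct the statement that AR(1) handles between-subject correlation. Add a random intercept for the camp attended, with a small-sample df correction (Kenward-Roger or Satterthwaite), at least as a pre-specified analysis, and report the camp variance.
3. **Data collection.** Record the camp attended and the facilitator team for each parent. A camp term cannot separate a facilitator effect if one team runs all the camps of an arm, so state how teams are assigned.
4. **Group size.** Reconcile the maximum of 25 in the synopsis BEM entry with the fixed 25 in the synopsis Study procedure and section 5.2, since this sets the number of camps.

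**Cost.** Wording and two data fields; correcting the analysis and the power statement needs no extra parents. The downside should be stated openly: with about six camps the camp variance is poorly estimated, and 4 df alone lowers unadjusted power to about 57% even at ICC 0 (about 72% on 10 df with six camps per arm). The stated power will be less favourable and the interval wider.
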